17.1 Sample size calculation

The primary objective of this trial is to compare the efficacy of thrice daily BIAsp 30 versus twice daily BIAsp 30, both in combination with metformin, in subjects with type 2 diabetes inadequately controlled on basal insulin combined with OADs. The primary endpoint is change from baseline in HbA_{1c} after 24 weeks of treatment and the sample size is determined based on this endpoint.

Let D be the mean treatment difference for change in HbA_{1c} (BIAsp 30 TID minus BIAsp 30 BID). The null-hypothesis will be tested against the alternative hypothesis as given by

$H_0: D = 0\%$ against $H_A: D \neq 0\%$

Sample size is determined using a t-statistic under the assumption of a two-sided test and a significance level of 5%. Based on experience from previous trials^{19,20}, an estimated treatment difference of 0.3% and a standard deviation (SD) of 1.1% for HbA_{1c} will be used in the sample size calculation (see [Table 17-1](#)). The randomisation scheme will be 1:1. The sample size calculation is done using Statistical Analysis System (SAS) 9.3.

Table 17–1 Number of subjects required totally under different SD and different power requirement

Subjects in total	Estimated SD in HbA _{1c} (%)			
	1.0	1.1	1.2	1.3
Power				
80%	352	426	506	592
85%	402	486	578	678
90%	470	568	676	792
95%	580	702	834	978

Assuming a SD of 1.1%, a total of 426 subjects (213 subjects per group) in the FAS analysis set will give 80% power in detecting the treatment difference between BIAsp 30 TID and BIAsp 30 BID based on the primary endpoint.

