6.1 Number of subjects

Number of subjects planned to be screened (i.e. documented informed consent): 610

Number of subjects planned to be randomised: 426

Number of subjects expected to complete the trial: 340

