6.5 Subject replacement

Subjects who are withdrawn will not be replaced.

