Presentation of results from a statistical analysis of a continuous endpoint analysed by a mixed model for repeated measurements (MMRM) analysis will include the estimated mean (= Least Square Mean) change from baseline for each treatment as well as the estimated mean treatment difference including a two-sided 95% confidence interval and a p-value for test of no difference between treatments.

If an assessment has been made both at screening and randomisation, and if not otherwise specified, the value from the randomisation visit will be used as the baseline value. If the value measured at the randomisation visit is missing and the assessment also has been made at screening, then the screening value will be used as the baseline value. If an assessment is only made at randomisation or at screening the relevant value will be the baseline value.

For efficacy variables missing values will not be replaced by imputed values unless otherwise specified. In the primary analysis missing values are handled by a MMRM.

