17.2 Definition of analysis sets

The following analysis sets are defined:

- Full Analysis Set (FAS): includes all randomised subjects who have been dosed and have any post randomisation data. The subjects and observations excluded from analysis sets, and the reason for this, will be described in the clinical trial report. The statistical evaluation of the FAS will follow the intention-to-treat (ITT) principle and subjects will contribute to the evaluation “as randomised”.
- Safety Analysis Set: includes all subjects receiving at least one dose of investigational product. Subjects in the safety set will contribute to the evaluation “as treated”.

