17.3 Primary endpoint

The primary objective of this trial is to compare the efficacy of thrice daily BIAsp 30 versus twice daily BIAsp 30, both in combination with metformin, in subjects with type 2 diabetes inadequately controlled on basal insulin combined with OADs.

The primary efficacy endpoint is the change from baseline in HbA_{1c} after 24 weeks of treatment. Change in HbA_{1c} from baseline to the 4, 8, 12, 16, 20 and 24 week’s measurements will be analysed using a Mixed Model for Repeated Measurements (MMRM), with treatment, combination of the two stratification factors (HbA_{1c} value and previous OAD treatment) and region (China/non-China)

as fixed factors and baseline HbA_{1c} as a covariate, all variables nested within visit as a factor. Region China includes China, Hong Kong and Taiwan and non-China includes all the other participating countries. An unstructured covariance matrix will be used to describe the variability for the repeated measurements for a subject. From the MMRM model the treatment difference at week 24 will be estimated and the corresponding 95% confidence interval and p-value will be calculated. All subjects in the FAS will be included in this analysis.

If p-value < 0.05, or equivalently, if the upper bound of the 95% confidence interval is below 0% or the lower bound of the 95% confidence interval is above 0%, the treatment difference will be regarded as statistically significant.

An important assumption for using MMRM is that the missing data are missing at random (MAR).

For this trial, missing data are mainly expected to occur due to withdrawal/discontinuation from the trial. Intermittent missing data (visits with missing data in between visits with data) is expected to be less common.

The main reasons for withdrawal/discontinuation are expected to be ineffective therapy and adverse events. Discontinuation due to ineffective therapy is expected to be MAR to some extent. For missing data due to adverse events, the MAR assumption may be questionable.

Sensitivity analyses will be performed for the primary efficacy endpoint. They will include:

- An analysis of covariance (ANCOVA) model with last observation carried forward (LOCF) imputation. Effects in the model are treatment, combination of the two stratification factors and region as factors, and baseline HbA_{1c} as a covariate.

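### The 80% power in Section 17.1 assumes a week-24 value from all 426 randomised subjects, but the plan expects 340 completers; at a residual SD of 1.1% the planned MMRM has about 71% to just under 80%

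*Combined protocol and SAP*

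**What the plan says.** Section 17.1 sizes the trial on the change in HbA1c at 24 weeks, with a difference of 0.3%, an SD of 1.1% and 1:1 allocation. The method is given as "Sample size is determined using a t-statistic under the assumption of a two-sided test and a significance level of 5" per cent. The conclusion is: "Assuming a SD of 1.1%, a total of 426 subjects (213 subjects per group) in the FAS analysis set will give 80% power". Table 17-1 varies only the SD and the power; it has no row or column for missing data.

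The other relevant statements are:

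- Section 6.1: "Number of subjects planned to be randomised: 426" and "Number of subjects expected to complete the trial: 340".
- Section 6.5: "Subjects who are withdrawn will not be replaced".
- Section 17 (general text): "In the primary analysis missing values are handled by a MMRM".
- Section 17.2, on the FAS: it "includes all randomised subjects who have been dosed and have any post randomisation data".
- Section 17.3: the primary test is the week-24 treatment difference from an MMRM over weeks 4, 8, 12, 16, 20 and 24, adjusted for baseline HbA1c, the combined strata and region. It adds: "For this trial, missing data are mainly expected to occur due to withdrawal/discontinuation from the trial".
- Section 8.1.7: for a withdrawn subject the investigator should try to carry out the Visit 26 procedures promptly. Nothing says whether an HbA1c taken then is used as the week-24 value.

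**The concern.** The number needed for 80% power and the number planned for randomisation are the same, 426. The t-test calculation treats every one of them as having a week-24 value, yet the plan itself expects about one in five not to complete and will not replace them.

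Stating the power for the FAS does not close the gap. A subject belongs to the FAS once dosed and with any data after randomisation, so membership does not imply a week-24 HbA1c. The FAS also cannot exceed the number randomised, so a FAS of 426 from 426 randomised leaves room for no exclusions.

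What is at stake is the type II error of the only primary test. If the trial gives a non-significant result, readers will judge it against a stated 80% that the plan has not shown to apply under its own completion figure.

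**Working it through.** **Inputs from the documents.** Difference 0.3%, SD 1.1%, two-sided 5%, 1:1 (Section 17.1); 426 randomised and 340 completing (Section 6.1); six post-baseline visits with unstructured covariance (Section 17.3).

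**Assumptions.** The loss is equal in the two arms, dropout is monotone, and 1.1% is the residual SD in the MMRM. Between-visit correlation and withdrawal timing are not given, so a range is used.

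**Step 1: reproduce the plan's figure.** For n per arm, the t-statistic has 2n − 2 degrees of freedom and noncentrality 0.3 / (1.1 × √(2/n)).

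- n = 213: noncentrality 2.815, power 80.2%.
- n = 212: power 79.998%, so 213 per arm is the smallest whole number that reaches 80%.

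All 16 cells of Table 17-1 reproduce. The table is correct for complete data, and the design has a margin of about one subject per arm.

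**Step 2: the expected loss.** 426 − 340 = 86; 86/426 = 20.2%; 43 per arm, leaving 340/2 = 170 completers per arm.

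**Step 3: lower bound.** If withdrawn subjects add nothing to the week-24 comparison, n = 170, the noncentrality is 2.514 and power is 70.8%. This would be the MMRM result if every withdrawal came before week 4 or the visits were uncorrelated. It is a floor, not a forecast.

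**Step 4: the planned MMRM.** For each arm, sum the information matrices of 170 complete subjects and 43 with truncated visit sequences, invert the sum, and take the week-24 diagonal element as the variance. Dividing the residual variance by that element gives the effective n per arm. Compound symmetry is written CS.

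| Withdrawal timing (assumed) | Correlation (assumed) | Effective n per arm | Power |
|---|---|---|---|
| All before week 4 | any | 170.0 | 70.8% |
| Even over weeks 0–24 | AR(1) 0.5 | 172.3 | 71.4% |
| Even over weeks 0–24 | CS 0.8 | 194.6 | 76.5% |
| Even over weeks 0–24 | CS 0.9 | 199.9 | 77.6% |
| At least one post-baseline value each | CS 0.9 | 205.7 | 78.8% |
| At least one post-baseline value each | CS 0.95 | 209.3 | 79.5% |
| All after week 20 | AR(1) 0.95 | 207.9 | 79.2% |
| All after week 20 | CS 0.95 | 209.8 | 79.6% |

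**Step 5: what would restore 80% at SD 1.1%.** An effective n of 212.0 per arm is needed. The share of week-24 variance that earlier visits must explain in the withdrawn subjects is

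(1/170 − 1/212.0) / (1/170 − 1/213) = 0.98,

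that is, a correlation of about √0.98 = 0.99.

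**Step 6: the residual SD at which 80% holds.** The last column is 1 − (SD/1.1)², the share of variance that the covariates would have to explain if 1.1% is an unadjusted SD.

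| Effective n per arm | Residual SD for 80% | Share explained |
|---|---|---|
| 170 | 0.98% | 20% |
| 180 | 1.01% | 15% |
| 190 | 1.04% | 10% |
| 200 | 1.07% | 6% |

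**The case against.** The strongest reply concerns the SD. Section 17.1 pairs 1.1% with a plain t-statistic, so it is natural to read it as an unadjusted SD. The MMRM then adjusts for baseline HbA1c, strata and region, a gain that Section 17.1 does not count. As an illustration, assume baseline HbA1c is uniform over the eligible 7.5–10.0% (SD 2.5/√12 = 0.72) and the slope of change on baseline is 0.5 in magnitude. Baseline then explains (0.5 × 0.72)²/1.1² = 11% of the variance. Power becomes 81.1% at an effective 194.6 per arm, although it is still only 75.6% at 170. This stands: on that reading a shortfall is not proven. But the plan does not state that reading, and the slope is not in the documents, so they do not support 80% either way.

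Other points on that side:

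- *Withdrawn subjects stay in the FAS and in the MMRM.* True, and this is why 70.8% is only a floor. It does not give them a week-24 value.
- *426 is a target, not a cap.* Section 7 lets subjects already screened when recruitment closes be randomised. Some overshoot is possible, but none is planned or counted.
- *The Visit 26 procedures at withdrawal will supply data.* Section 18.4 keeps such data for the trial report, but no section assigns that HbA1c to week 24 in the model.
- *The sum is not wrong.* Agreed. Table 17-1 is right for complete data; what is missing is the link from that case to the completion the plan expects.
- *The result will be read from its confidence interval.* Partly so. The protocol still states 80% without a completion condition.

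**Conclusion.** The concern holds. With the plan's own 340 completers and 1.1% as the residual SD, the primary MMRM has between 70.8% and just under 80% power, so the type II error is between just over 20% and 29%, against the 20% implied. No scenario examined reached 80%. The two bounds are firm under equal loss per arm. The position between them cannot be fixed from the documents, because correlation and withdrawal timing are not given. The conclusion is conditional on the SD: if 1.1% is unadjusted and covariates explain some 6% to 20% of the variance, depending on how much the MMRM recovers, 80% is attainable. The test, its type I error and the estimate are not affected.

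**What to change.** Amend Section 17.1 as follows:

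1. Say that 80% applies to 426 subjects with complete week-24 data.
2. Give the power with 340 completers: about 71% to just under 80% for the MMRM at a residual SD of 1.1%, with the between-visit correlation and withdrawal timing assumed.
3. Say whether 1.1% is the SD before or after covariate adjustment.
4. If 80% is to be kept as the headline, state the residual SD at which it holds (about 0.98% if only completers contribute; about 1.04% to 1.07% if the MMRM recovers the equivalent of 190 to 200 per arm) and justify it.
5. Say whether an HbA1c taken under Section 8.1.7 enters the model as a week-24 value.

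The cost is wording. Enrolment and the analysis stay as they are. The stated power becomes a range, less favourable than 80% unless an adjusted SD is justified.

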17.2 Definition of analysis sets

The following analysis sets are defined:

- Full Analysis Set (FAS): includes all randomised subjects who have been dosed and have any post randomisation data. The subjects and observations excluded from analysis sets, and the reason for this, will be described in the clinical trial report. The statistical evaluation of the FAS will follow the intention-to-treat (ITT) principle and subjects will contribute to the evaluation “as randomised”.
- Safety Analysis Set: includes all subjects receiving at least one dose of investigational product. Subjects in the safety set will contribute to the evaluation “as treated”.

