5.1 Type of trial

[figure not shown]
This is an open-labelled, randomised, two-armed, parallel group, multinational, multicentre, treat-to-target trial. It consists of a screening period (of up to 2 weeks) a 24-week treatment period and 30-day follow-up period ([Figure 5–1](#)).

Randomisation will be stratified according to HbA_{1c} value and pre-trial OAD treatment. The strata correspond to the HbA_{1c} intervals of 7.5%–8.5% (both inclusive) and 8.6%–10.0% (both inclusive). The strata regarding OADs are: metformin monotherapy and metformin + one additional OAD.

The eligible subjects will be randomised in a 1:1 manner into one of the two arms with the following treatment:

- BIAsp 30 TID + metformin
- BIAsp 30 BID + metformin

Within each participating country it will be aimed at including a maximum of 20% of randomised subjects on treatment with NPH prior to screening (Visit 1).

n: number of subjects to be randomised; V: Visit; W: Week; EOT: end-of-treatment; FU: follow-up

Figure 5–1 Trial design

Subjects must continue metformin throughout the trial and any other OAD should be discontinued at randomisation (Visit 2).

The insulin dose will be titrated on a weekly basis for all subjects throughout the trial. Titration will be performed according to a titration algorithm for BIAsp 30 in order to achieve the pre-meal SMPG target of 4.4–6.1 mmol/L (80–110 mg/dl) (refer to [Appendix A](#)).

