5.3 Treatment of subjects

In this trial, BIAsp 30 is classified as Investigational Medicinal Products (IMP).

At randomisation the subjects' pre-trial basal insulin and OAD treatments (except for metformin) will be discontinued. The eligible subjects will be randomised in a 1:1 ratio to receive trial treatment of BIAsp 30 TID or BID, both in combination with metformin.

5.3.1 BIAsp 30

Subjects randomised to the BIAsp 30 TID arm will receive BIAsp 30 before breakfast, lunch and main evening meal. Subjects randomised to the BIAsp 30 BID arm will receive BIAsp 30 before breakfast and main evening meal.

The total daily dose of pre-trial basal insulin should be transferred to the total daily starting dose of BIAsp 30 by unit-to-unit, which will be distributed along meals at the investigator's discretion.

During the 24-week treatment period, the insulin dose will be individually titrated on a weekly basis for all subjects in accordance with the titration guideline described in [Appendix A](#) in order to achieve the pre-meal SMPG target of 4.4–6.1 mmol/L (80–110 mg/dL)⁶.

An independent Novo Nordisk Titration Group will centrally perform insulin titration surveillance as described in Section [14.2](#).

BIAsp 30 should be administered as s.c. injections according to the locally approved label and as described in the Direction For Use (DFU). The chosen region of the body where the injection is to be administered should remain the same throughout the trial. However, the injection site within the chosen body region should rotate or change for each administration.

For further details, please refer to the titration guideline in [Appendix A](#).

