11.1 Breaking of blinded codes

This is an open-label trial. Breaking of blinded codes is not applicable for this trial.

12 Adverse events, and technical complaints and pregnancies

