The dichotomous endpoints will be analysed by a logistic regression model. Effects in the model are treatment, combination of the two stratification factors and region as factors, and baseline HbA_{1c} as a covariate. The results will include the 95% confidence interval for the odds ratio (BIAsp 30 TID

over BIAsp 30 BID) and the p-value for test of no difference between the groups as part of the presentation.

For the dichotomous endpoint of HbA_{1c}<7% at week 24 (yes/no), missing HbA_{1c} values at week 24 will be imputed using the predicted value from an MMRM analysis. For the other two dichotomous endpoints, as a conservative approach, subjects withdrawn before 24 weeks will be handled as non-responders.

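### The full analysis set is a modified ITT set that drops never-dosed subjects; in this open-label trial that could slightly bias the two non-responder endpoints

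*Combined protocol and SAP*

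**What the plan says.** Section 17.2 admits to the FAS only subjects meeting two conditions that arise after randomisation: it "includes all randomised subjects who have been dosed and have any post randomisation data". The same paragraph adds: "The statistical evaluation of the FAS will follow the intention-to-treat (ITT) principle and subjects will contribute to the evaluation" as randomised. It also commits to disclosure: "The subjects and observations excluded from analysis sets, and the reason for this, will be described in the clinical trial report".

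Section 17.3 runs the primary mixed model for repeated measurements (MMRM) on this set: "All subjects in the FAS will be included in this analysis". Section 17.4.1.1 names no analysis set for the responder endpoints, but the FAS is the only efficacy set defined. For two of the three responder endpoints, HbA1c below 7.0% without severe hypoglycaemia and the same without severe or BG confirmed hypoglycaemia, the rule is: "as a conservative approach, subjects withdrawn before 24 weeks will be handled as non-responders". Section 4.2.2.1 marks the first of these as a key supportive endpoint chosen for registry posting.

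On what the subject knows, section 11.1 states: "This is an open-label trial". Under section 5.3.1, "Subjects randomised to the BIAsp 30 TID arm will receive BIAsp 30 before breakfast, lunch and main evening meal", while the BID arm injects before breakfast and the main evening meal only. Section 8.1.5 places the randomisation session and the training in trial product use at Visit 2, and section 9.4 has the first pens dispensed there. The arm is therefore known before the first dose.

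**The concern.** A subject who declines on learning the allocation is never dosed and so leaves the FAS. Three injections a day, one of them at lunch, is the heavier regimen, so such refusals could be more frequent in the TID arm.

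The responder endpoints are where this matters. A subject who refuses the allocated regimen is the plainest case for a non-responder rule, yet the FAS takes that subject out of the denominator before the rule applies. The responder proportion then rises in whichever arm has more refusals, which is the opposite of conservative.

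The dosing condition applies even when data exist. Section 8.1.7 asks for Visit 26 procedures in withdrawn subjects and section 18.4 retains the results, but an undosed subject with such data would still be excluded. The control-based imputation in section 17.3, described there as imitating an ITT scenario, also omits these subjects.

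**Working it through.** **The plan's own figure.** Inputs from section 17.1: difference 0.3, SD 1.1, two-sided 5%, 1:1 allocation, 80% power. A two-sample t-test with the noncentral t distribution needs 213 per arm, 426 in total, with power 80.2%. The stated 426 reproduces exactly, as do all 16 cells of Table 17-1.

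**Room for exclusions.** Section 17.1 counts 426 in the FAS, section 6.1 plans to randomise 426, and section 6.5 rules out replacement, so the plan assumes no exclusions. It gives no expected number, so the following shares of the 426 are assumed:

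- Excluded 1%, 2%, 3%, 5%: power 79.8%, 79.4%, 79.0%, 78.1%.
- Number to randomise to keep 426 in the FAS, 426/(1 − share): 431, 435, 440, 449.

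**Primary endpoint.** If only TID subjects are excluded, the difference among all randomised subjects departs from the FAS difference by (excluded share of the arm) × (gap in mean HbA1c change between excluded and retained subjects). With an assumed gap of 0.5 to 1.0 points:

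- 1% of the arm (about 2 subjects): 0.005 to 0.010.
- 2% (about 4): 0.010 to 0.020, at most 0.020/0.3 = 6.7% of the planning effect.
- 5% (about 11): 0.025 to 0.050, at most 0.050/0.3 = 16.7%.

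The standard error of the difference is 1.1 × √(2/213) = 0.107. Under the null, the two-sided rejection rate is 5.4% at a shift of 0.020 and 7.5% at 0.050. Redefining the FAS would not by itself move the MMRM, because a subject with no post-baseline HbA1c contributes no change score.

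**Non-responder endpoints.** Assumptions: 40% of dosed subjects respond in both arms, every BID subject is dosed, and undosed TID subjects count as non-responders. The calculation is unadjusted, whereas the planned logistic model is adjusted.

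- FAS: 40% against 40%, odds ratio 1.00.
- BID odds: 0.40/0.60 = 0.667.
- 4 of 213 TID undosed (2%): 0.40 × 209/213 = 39.2%, odds 0.646, odds ratio 0.646/0.667 = 0.97.
- 11 of 213 TID undosed (5%): 0.40 × 202/213 = 37.9%, odds 0.611, odds ratio 0.611/0.667 = 0.92.
- Standard error of the log odds ratio: √(2/(213 × 0.40 × 0.60)) = 0.198.
- Shift: |ln 0.969|/0.198 = 0.16 and |ln 0.917|/0.198 = 0.44 standard errors.

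If BID also loses subjects, the shift shrinks. With 4 undosed in BID and 11 in TID, the odds ratio is 0.611/0.646 = 0.95.

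**Reach of the imputation.** The control-based steps in section 17.3 first fill intermittent gaps, then impute week 8 from a control-group model that conditions on week-4 HbA1c, then continue visit by visit. No step covers a subject with no post-baseline HbA1c. This affects never-dosed subjects and also dosed subjects who leave before week 4, who are already in the FAS.

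**The case against.** The case for leaving the definition alone has real weight.

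- **The exclusion is narrow.** Post-randomisation data of any kind suffice, not HbA1c alone, and contacts are weekly from week 1. Hardly any dosed subject would be lost, so never being dosed is the only realistic route.
- **Refusal is screened for.** Inclusion criteria 8 and 9 require willingness to eat three main meals and to comply with the injection regimen, and section 8.1.5 has all criteria rechecked at Visit 2. Section 17.3 expects withdrawals mainly for ineffective therapy and adverse events.
- **BID also adds burden.** Subjects on a basal analogue enter on one injection a day, so refusals need not fall in TID alone.
- **Exclusions will be disclosed** with reasons in the trial report.

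These points limit the size of the problem without removing it. The screens lower the chance of refusal but cannot exclude it, and a description of exclusions does not restore the randomised comparison.

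A reader might go further and infer that the trial delivers no ITT evaluation at all. The documents do not support that: section 17.2 applies the principle within the FAS, analyses subjects as randomised and discloses who is left out. Nor do they support reading section 17.1 as a sample-size error. The 426 is correct, and exclusions of 1% to 2% leave power at 79.4% or above.

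**Conclusion.** The FAS is a modified ITT set. Entry depends on events after an open allocation, and no planned analysis includes everyone randomised. The two non-responder endpoints could be slightly biased in favour of the arm with more early refusals: on the assumptions above, an odds ratio of 1.00 in the FAS against 0.97 to 0.92 among all randomised subjects, or 0.16 to 0.44 standard errors.

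That size rests on a 40% response rate and on 2% to 5% never dosed in TID alone, none of which the documents give. Arm-dependent refusal is plausible, not shown, so the statement is that bias could arise, not that it is present. The primary result is little affected; a material shift needs about 5% lost from one arm together with a gap near 1 HbA1c point. This is a modest point, worth acting on because the remedy is cheap.

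**What to change.** 1. In section 17.2, define the FAS as all randomised subjects, analysed as randomised. At the least, analyse the two non-responder endpoints on all randomised subjects.
2. In section 17.4.1.1, name the analysis set and state that undosed subjects, and those with no post-randomisation data, count as non-responders in those two endpoints.
3. Report the number randomised but not dosed, by arm.
4. In section 17.3, add a week-4 step to the control-based imputation: a control-group model conditional on baseline HbA1c, the combined strata and region, applied to both arms. Changing section 17.2 alone cannot bring never-dosed subjects into this analysis. The step also covers dosed subjects who leave before week 4.
5. Keep the dosing requirement for the safety analysis set.

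The cost is slightly lower responder proportions and one extra imputation step. If the FAS itself is changed, never-dosed subjects also enter the simple HbA1c below 7.0% endpoint, where the planned MMRM prediction would rest on their arm and baseline covariates alone. The minimum option in item 1 avoids this.
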